4.2. Treatment Discontinuation

Treatment discontinuation occurs when a subject is no longer receiving study drug(s).

Note that treatment discontinuation is not the same as study withdrawal. A subject should be discontinued from study treatment if, in the opinion of the investigator, it is medically necessary, or if it is the wish of the subject. All subjects who discontinue study treatment should enter safety follow-up followed by survival follow-up; if a subject discontinues study treatment prior to confirmed progression of disease, the subject will continue to be followed for disease progression as per the planned study visits and procedures.

Subjects will be discontinued from study treatment for any the following reasons:

- An AE that requires permanent discontinuation of study drug(s).
- Confirmed progression of disease (Note: subjects may continue treatment beyond RECIST v1.1 determined PD).
- Noncompliance with protocol.
- Investigator decision.
- Subject becomes pregnant.
- Subject death.
- Subject lost to follow-up.
- Termination of the study by the sponsor.
- Voluntary withdrawal from the study treatment by the subject.

4.3. Method of Treatment Assignment

Upon enrollment, subjects will be assigned a unique number in ascending numerical.

4.4. Preparation/Handling/Storage/Accountability

1. The investigator or designee must confirm appropriate temperature conditions have been maintained during transit for all study treatment received and any discrepancies are reported and resolved before use of the study treatment.
2. Store etigilimab and nivolumab under refrigeration at 2°C to 8°C (36°F to 46°F). Protect nivolumab from light by storing in the original package until time of use. Do not freeze or shake.
3. The diluted etigilimab solution may be stored for no more than 8 hours at room temperature or at 2°C- 8°C for up to 48 hours.
4. Only subjects enrolled in the study may receive study treatment and only authorized site staff may supply or administer study treatment. All study treatments must be stored in a secure, environmentally controlled, and monitored (manual or automated) area in accordance with the labeled storage conditions with access limited to the investigator and authorized site staff.
5. Any unused portion left in a vial may not be used for another subject, as the product contains no preservative (ie, they are single-use vials).

6. The investigator, institution, or the head of the medical institution (where applicable) is responsible for study treatment accountability, reconciliation, and record maintenance (ie, receipt, reconciliation, and final disposition records).
7. Further guidance and information for the final disposition of unused study treatment are provided in the Pharmacy Manual.

4.5. Treatment Compliance

Etigilimab and nivolumab are administered IV by study site personnel. Thus, compliance with each infusion will be documented in the subject's medical records and then recorded on the appropriate electronic case report form (eCRF) screen. In addition, drug accountability and PK monitoring will be done.

- Dates of administration including start and end dates.
- Dosage information including dose and frequency.
- Appropriate information to assess any potential vaccine- related AEs.

Subjects who experience infusion-associated symptoms may be treated symptomatically with acetaminophen, ibuprofen, diphenhydramine, and/or cimetidine or another H2 receptor antagonist, as per standard practice (for sites outside the U.S., equivalent medications may be substituted per local practice). Serious infusion-associated events manifested by dyspnea, hypotension, wheezing, bronchospasm, tachycardia, reduced oxygen saturation, or respiratory distress should be managed with supportive therapies as clinically indicated (e.g., supplemental oxygen and β 2-adrenergic agonists). Premedication may be administered for Cycles ≥ 2 at the discretion of the treating physician after consultation with the Medical Monitor.

Subjects are permitted the use of topical, ocular, intra-articular, intranasal, and inhalational corticosteroids (with minimal systemic absorption). Adrenal replacement steroid doses >10 mg daily prednisone are permitted. A brief (single dose up to less than 3 weeks) course of corticosteroids for prophylaxis (e.g., contrast dye allergy) or for treatment of non-autoimmune conditions (e.g., delayed-type hypersensitivity reaction caused by a contact allergen) is permitted. Systemic corticosteroids >10 mg daily, TNF α antagonists, and other immunosuppressive agents may attenuate potential beneficial immunologic effects of treatment with etigilimab and nivolumab but may be administered at the discretion of the treating physician in an emergency or after consultation with the Medical Monitor. If feasible, alternatives to corticosteroids should be considered. The use of inhaled corticosteroids and mineralocorticoids (eg, fludrocortisone for subjects with orthostatic hypotension or adrenocortical insufficiency) is allowed. Physiologic doses of corticosteroids for adrenal insufficiency are allowed. Megestrol administered as an appetite stimulant is also permitted.

Subjects who use oral contraceptives, hormone-replacement therapy, prophylactic or therapeutic anticoagulation therapy (such as low molecular weight heparin or warfarin at a stable dose level), or other maintenance therapy for non-malignant indications should continue their use.

The Medical Monitor should be contacted if there are any questions regarding concomitant or prior therapy.

5. DISCONTINUATION, DOSE HOLD, AND RESUMPTION

Subjects will be monitored continuously for toxicity while on study treatment. Toxicity will be assessed using the NCI CTCAE version 5.0 or higher.

If a subject has an AE related to etigilimab and/or nivolumab then dose interruptions/holds may occur as described below.

5.1. Etigilimab Dose Holds and Discontinuation

Permanent Discontinuation Criteria for Etigilimab

Dosing with etigilimab should be permanently discontinued for the following toxicities:

- \geq Grade 4 neutropenia persisting for \geq 7 days and/or complicated by infection febrile neutropenia.
- \geq Grade 4 thrombocytopenia.
- Grade 3 drug-related thrombocytopenia $>$ 7 days or associated with clinically significant bleeding requires discontinuation.
- Any \geq Grade 3 non-hematologic toxicity, except:
 - Grade 3 fatigue lasting $<$ 7 days.
 - Grade 3 nausea, emesis, or diarrhea responding to supportive treatment within 5 days.
- Grade 3 drug-related AE of the skin requires dose discontinuation.
- \geq Grade 3 non-hematological laboratory abnormalities do not require treatment discontinuation except:
 - Grade \geq 3 AST, ALT, total bilirubin requires dose discontinuation
 - Concurrent AST or ALT $>$ 3 x ULN and total bilirubin $>$ 2 x ULN requires permanent dose discontinuation.

Note: In most cases of Grade 3 AST or ALT elevation, study treatment will be permanently discontinued. If the investigator determines a possible favorable benefit/risk ratio that warrants continuation of study treatment, a discussion between the investigator and the Medical Monitor or designee must occur.

- Isolated Grade 4 electrolyte imbalances/abnormalities that are not associated with clinical sequelae and are corrected with supplementation/appropriate management within 72 hours of their onset.

Etigilimab may be held/delayed due to toxicity. The dose level of etigilimab will not be modified for individual subjects in this study.

Dose Delay Criteria for Etigilimab

- Grade 2 non-skin, drug-related AE, except for fatigue.
- Grade 2 drug-related creatinine, AST, ALT, and/or total bilirubin abnormalities.
- Grade 3 skin drug-related AE.
- Grade 3 drug-related laboratory abnormality with the following exceptions:
 - Grade 3 lymphopenia or asymptomatic amylase or lipase does not require a dose delay.
- Any AE, laboratory abnormality or inter-current illness which, in the judgment of the investigator, warrants delaying the dose of study medication.

The maximum duration of a dose hold is 28-days, unless a longer hold is approved by the Medical Monitor or designee; thereafter, the subject should be discontinued from etigilimab treatment. Etigilimab infusions may be delayed to allow subjects to recover from study treatment related AEs or intercurrent illness. Subjects who require delay of etigilimab should be re-evaluated weekly or more frequently if clinically indicated and resume etigilimab dosing when re-treatment criteria are met (see below) following discussion with the Medical Monitor. Individual subject cases should be discussed with the Sponsor Medical Monitor or designee for individual treatment decisions.

Dosing visits are not skipped, only delayed. Tumor assessments should continue as per protocol even if dosing is delayed.

Criteria to Resume Etigilimab Dosing

- Subjects will be permitted to resume etigilimab therapy following resolution of the AE to \leq Grade 1 or to baseline value, with the following exceptions.
- Subjects may resume treatment in the presence of Grade 2 fatigue.
- Subjects who have not experienced a Grade 3 drug-related skin AE may resume treatment in the presence of Grade 2 skin toxicity.
- For subjects with Grade 2 AST, ALT, and/or total bilirubin abnormalities, dosing may resume when laboratory values return to baseline and management with corticosteroids, if needed, is complete (See Appendix 8).
- Drug-related pulmonary toxicity, diarrhea, or colitis must have resolved to baseline before treatment is resumed. Subjects with persistent Grade 1 pneumonitis after completion of a steroid taper over at least 1 month may be eligible for retreatment if discussed with and approved by the Medical Monitor or designee.
- Subjects with drug-related endocrinopathies adequately controlled with only physiologic hormone replacement may resume treatment after consultation with the Medical Monitor or designee. Adrenal insufficiency requires discontinuation regardless of control with hormone replacement.

Subjects who meet criteria for permanent discontinuation must not receive further study therapy.

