4. TREATMENTS

Study treatment is defined as any investigational treatment(s), marketed product(s), placebo, or medical device(s) intended to be administered to a study subject according to the study protocol.

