5.2. Nivolumab Dose Hold, Resumption and Discontinuation

Nivolumab may be held/interrupted due to toxicity. The dose level of nivolumab will not be modified in this study. Repeat nivolumab infusions may be delayed to allow subjects to recover from study treatment related AEs or intercurrent illness. Dosing visits are not skipped, only delayed. Tumor assessments should continue as per protocol even if dosing is delayed.

A pattern of immune-related AEs has been defined for nivolumab treatment for which management algorithms have been developed ([OPDIVO 2018](#)). Most high- grade events were manageable with dose delays and the use of corticosteroids or hormone replacement therapy (endocrinopathies) as instructed in these algorithms.

Details on dose delays, re-initiation of treatment and discontinuation of nivolumab are provided below.

Dose Delay Criteria for Nivolumab

Nivolumab administration should be delayed for the following:

- Grade 2 non-skin, drug-related AE, except for fatigue.
- Grade 2 drug-related creatinine, AST, ALT and/or total bilirubin abnormalities.
- Grade 3 skin drug-related AE.
- Grade 3 drug-related laboratory abnormality with the following exceptions:
 - Grade 3 lymphopenia or asymptomatic amylase or lipase does not require a dose delay.
 - Grade ≥ 3 AST, ALT, total bilirubin required dose discontinuation (see below).
- Any AE, laboratory abnormality or inter-current illness which, in the judgment of the investigator, warrants delaying the dose of study medication.

Subjects who require delay of nivolumab should be re-evaluated weekly or more frequently if clinically indicated and resume nivolumab dosing when re-treatment criteria are met (see below).

If the decision is to resume nivolumab dosing, the subject should restart treatment on the next regularly scheduled dosing visit. Skipped doses are not to be replaced. If treatment is delayed >8 weeks, the subject may potentially be permanently discontinued from all study therapy, except as specified in the treatment discontinuation criteria below. Individual subject cases should be discussed with the Medical Monitor or designee for individual treatment decisions.

Criteria to Resume Nivolumab Dosing

Subjects will be permitted to resume nivolumab therapy following resolution of the AE to \leq Grade 1 or to baseline value, with the following exceptions:

- Subjects may resume treatment in the presence of Grade 2 fatigue.

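### Protocol 5.1 makes a Grade 3 drug-related skin AE both a permanent stop and a dose delay for etigilimab, and prints a corrected Grade 4 electrolyte abnormality under the permanent-stop heading

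*Protocol*

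**What the plan says.** Protocol 5.1 has three lists for etigilimab: permanent discontinuation, dose delay and resumption.

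- **Stop list.** A dedicated bullet reads "Grade 3 drug-related AE of the skin requires dose discontinuation". A general bullet applies at or above "Grade 3 non-hematologic toxicity, except", and its only exceptions are short-lived fatigue and treatable nausea, emesis or diarrhea.
- **Delay list.** One entry reads, in full, "Grade 3 skin drug-related AE".
- **Resume list.** One bullet says "Subjects who have not experienced a Grade 3 drug-related skin AE may resume treatment in the presence of Grade 2 skin toxicity". The section closes with "Subjects who meet criteria for permanent discontinuation must not receive further study therapy".

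The stop list ends with a bullet on isolated Grade 4 electrolyte abnormalities that have no clinical sequelae and are corrected within 72 hours. No exception wording introduces it.

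Section 5.1 also provides for case discussion: "Individual subject cases should be discussed with the Sponsor Medical Monitor or designee for individual treatment decisions".

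**The concern.** These are operative dosing rules. A site with a subject who has a Grade 3 drug-related skin AE can find an instruction to end etigilimab and an instruction to hold it, in the same section and with nothing to separate the cases. The protocol does not say which list governs. Read literally, the electrolyte bullet ends treatment for a laboratory change that was harmless and has already been corrected.

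What is at stake is consistent handling of subjects across sites. There is also one reporting question. Protocol 8.8 requires a record of cases in which therapy went on although it should have been stopped. Whether re-dosing after a Grade 3 skin AE is such a case depends on which bullet is applied.

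**Working it through.** The plan states no figure on this point, so the check compares the text of 5.1 with the parallel nivolumab rules in 5.2.

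**Skin AE, Grade 3, drug-related**

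| Rule | Etigilimab (5.1) | Nivolumab (5.2) |
|---|---|---|
| Dedicated stop bullet | Yes | No |
| General Grade 3 stop rule | Covers skin, which is not among the exceptions | Limited to non-skin AEs |
| Delay list | Yes, unqualified | Yes |
| Resume bullet on Grade 2 skin toxicity | Yes | Yes, same words |

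1. In 5.2 the entries fit together. A Grade 3 skin AE delays nivolumab, it is outside the general Grade 3 stop rule, and the resume bullet distinguishes subjects who have had one from those who have not.
2. In 5.1 they do not. Two entries say stop and one says delay, for the same event at the same grade. The entries stand under separate headings, so lost indentation cannot explain the conflict.
3. Under a stop rule the 5.1 resume bullet still has a use, for subjects held for another reason who have Grade 2 skin toxicity. Only its condition about a previous Grade 3 skin AE becomes redundant, since every such subject has already stopped. With the matching delay line, this suggests that text was carried over from the nivolumab section.
4. The closing sentence of 5.1 bars further therapy once a stop criterion is met, so it favours the stop reading. It does not remove the delay line.

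**Electrolytes, isolated Grade 4, no sequelae, corrected within 72 hours**

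1. In 5.1 the item stands under the heading for permanent discontinuation. As an outer bullet it is a stop. As a further item under the laboratory rule's exceptions it is also a stop, because that rule says such abnormalities do not require discontinuation unless excepted.
2. In 5.2 the same wording appears among the Grade 4 events that do not require nivolumab to be discontinued.
3. Taken literally, the 5.1 laboratory rule would name the corrected, harmless electrolyte abnormality as a stop and leave the uncorrected one unnamed. That cannot be the intent. The item is almost certainly an exception in the wrong place.

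**Effect on reporting**

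1. SAP Listing 16.2.7 records the action actually taken for each drug, and the shell of Table 14.3.1.1 counts doses held, interrupted and discontinued by drug. These counts follow what was done, not which rule was correct.
2. ORR and the Simon rules make no use of these criteria.
3. What remains is the deviation category in Protocol 8.8, with important deviations reviewed at the data review meeting under SAP 10.3.

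**The case against.** The strongest reply is that the text mostly points one way. Two stop entries and the closing sentence outweigh one delay line, so a careful reader would stop. Section 5.1 also lets a delayed subject resume etigilimab only after discussion with the Medical Monitor, so a site should not restart on its own reading. Both points stand, and they limit the practical divergence. They do not cure the conflict: if stop governs, the delay line is dead text that still tells a site to hold the dose, and a duty to discuss the case does not say which rule applies.

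On electrolytes, one can fairly answer that the list was read from a PDF, that a note interrupts it just before this bullet, and that another bullet in the same list states what does not require stopping. That supports treating the item as a drafting slip rather than a realistic route to ending treatment. It still needs to be moved.

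A reader might take the resume bullet as a second contradiction. It is not one, because under a stop rule only its Grade 3 condition loses its function.

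A reader might also infer that the closing sentence of 5.1 takes a subject with a Grade 3 skin AE off nivolumab as well. The documents do not settle that. Section 4 defines study treatment broadly, and 5.2 writes "permanently discontinued from all study therapy" in one place, but neither text ties the closing sentence to one drug or to both. The Appendix 8 skin algorithm might bear on it, but its figure is not available here. No finding is made on that question.

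**Conclusion.** The point holds as a minor internal inconsistency in the safety rules. The double listing of the Grade 3 skin AE is certain on the face of the text. That the electrolyte bullet is a misplaced exception is an inference, strongly supported by 5.2.

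The number of subjects affected cannot be derived. The documents give no Grade 3 skin AE rate. The earlier study, summarised in Protocol 1.2, names pruritus and several forms of rash among the most common immune-related events but does not give their grades. An assumed rate would only produce a range too wide to be useful.

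A reader might infer that safety tables or efficacy results are distorted. The documents do not support this: actions are recorded as taken, and no efficacy endpoint or Simon boundary depends on these criteria.

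**What to change.** 1. **Skin, if stopping is intended (the reading the text favours).** In 5.1, delete "Grade 3 skin drug-related AE" from the etigilimab delay list. Drop the opening condition of the skin resume bullet, so that it simply allows resumption with Grade 2 skin toxicity.
2. **Skin, if delay is intended.** Delete the dedicated skin stop bullet, add a Grade 3 drug-related skin AE to the exceptions of the general non-hematologic rule, and state that Grade 4 remains a stop. Keep the delay line and the resume bullet.
3. **Electrolytes.** Move the bullet to an explicit list of events that do not require discontinuation, as 5.2 does.
4. **Leave the nivolumab skin bullets in 5.2 unchanged.**
5. **Analysis stage.** SAP 6.3 says that the study was terminated. At the data review meeting, list any etigilimab re-dosing after a Grade 3 skin AE and note that the protocol text conflicts. Do not class it automatically as a deviation: that would penalise investigators who followed the printed delay criterion.

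The cost of option 1 with item 3 is one bullet deleted, one shortened and one moved. Option 2 with item 3 is one bullet deleted, one exception added and one bullet moved. Under Appendix 3 a protocol amendment needs ethics approval, so with the study terminated the rewording may matter mainly for later protocols that reuse this text. The data review step costs a short listing and a line in the minutes. Endpoints, sample size, Simon rules and tables do not change.

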- Subjects who have not experienced a Grade 3 drug-related skin AE may resume treatment in the presence of Grade 2 skin toxicity.

- For subjects with Grade 2 AST, ALT, and/or total bilirubin abnormalities, dosing may resume when laboratory values return to baseline and management with corticosteroids, if needed, is complete.
- Drug-related pulmonary toxicity, diarrhea or colitis must have resolved to baseline before treatment is resumed. Subjects with persistent Grade 1 pneumonitis after completion of a steroid taper over at least 1 month may be eligible for retreatment if discussed with and approved by the Medical Monitor or designee.
- Subjects with drug-related endocrinopathies adequately controlled with only physiologic hormone replacement may resume treatment after consultation with the Medical Monitor or designee. Adrenal insufficiency requires discontinuation regardless of control with hormone replacement.
- Subjects who meet criteria for permanent discontinuation must not receive further study therapy.

Permanent Treatment Discontinuation Criteria for Nivolumab

Subjects meeting any of the following criteria will be required to permanently discontinue nivolumab:

- Any Grade 2 drug-related uveitis or eye pain or blurred vision that does not respond to topical therapy and does not improve to Grade 1 severity within 8 weeks OR requires systemic treatment.
- Any Grade 3 non-skin, drug-related AE lasting >7 days or recurs, with the following exceptions for laboratory abnormalities, drug-related uveitis, pneumonitis, bronchospasm, neurologic toxicity, hypersensitivity reactions, infusion reactions, and endocrinopathies:
 - Grade 3 drug-related uveitis, pneumonitis, bronchospasm, neurologic toxicity, myocarditis, hypersensitivity reaction, or infusion reaction **of any duration** requires discontinuation.
 - Grade 3 drug-related endocrinopathies adequately controlled with only physiologic hormone replacement do not require discontinuation. Adrenal insufficiency requires discontinuation regardless of control with hormone replacement.
- Grade 3 drug-related laboratory abnormalities do not require treatment discontinuation except:
 - Grade 3 drug-related thrombocytopenia >7 days or associated with clinically significant bleeding requires discontinuation.
 - Grade ≥ 3 drug-related AST, ALT, or total bilirubin requires discontinuation.
 - Concurrent AST or ALT $>3 \times$ ULN and total bilirubin $>2 \times$ ULN.

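### Section 5.1 lists a Grade 3 drug-related skin AE as both a permanent stop and a dose delay for etigilimab, and carries what is probably a misplaced electrolyte exemption under the permanent-stop heading

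*Protocol*

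**What the plan says.** Protocol Section 5.1 opens its stop list with "Dosing with etigilimab should be permanently discontinued for the following toxicities". Two bullets under that heading cover a Grade 3 drug-related skin event. One names it: "Grade 3 drug-related AE of the skin requires dose discontinuation". The other is general, "Grade 3 non-hematologic toxicity, except", and its only exceptions are short-lived fatigue and nausea, emesis or diarrhea that responds to supportive care.

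The etigilimab dose-delay list in the same section contains "Grade 3 skin drug-related AE". The resume criteria set a default of recovery to Grade 1 or baseline and then list exceptions, one of which reads "Subjects who have not experienced a Grade 3 drug-related skin AE may resume treatment in the presence of Grade 2 skin toxicity". The section closes with "Subjects who meet criteria for permanent discontinuation must not receive further study therapy".

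The last bullet under the stop heading is "Isolated Grade 4 electrolyte imbalances/abnormalities that are not associated with clinical sequelae", with the further condition that the value is corrected within 72 hours. Earlier in the same list, a laboratory bullet says that non-hematological laboratory abnormalities of Grade 3 or higher do not call for a stop, apart from two items on AST, ALT and bilirubin.

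Section 5.2 has the same skin item in its nivolumab delay list, but its Grade 3 stop rule is limited: "Any Grade 3 non-skin, drug-related AE lasting" more than 7 days, or recurring. It uses the electrolyte sentence as one of the Grade 4 events that do not require nivolumab to be stopped.

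**The concern.** Stop and delay are mutually exclusive actions for one event and one drug. A site that reads the delay list would hold etigilimab for a Grade 3 skin AE and plan to restart. A site that reads the stop list would end etigilimab for good. Protocol Section 8.8 requires therapy continued past a required stop to be recorded as a deviation and summarised in the final report, so the text bears on safety conduct and on deviation coding.

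The electrolyte line raises a related problem. Taken at face value under its heading, it ends etigilimab for a laboratory value that caused no harm and has been corrected, while the same sentence protects nivolumab dosing in the next section.

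**Working it through.** No arithmetic beyond a count of rules applies. The check sets the lists side by side.

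**Skin event (Grade 3, drug-related)**

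| Rule | Etigilimab (5.1) | Nivolumab (5.2) |
|---|---|---|
| Event-specific permanent-stop bullets | 2 (skin bullet; general non-hematologic bullet) | 0 (the Grade 3 stop is for non-skin events) |
| Dose-delay bullets | 1 | 1 |

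The nivolumab count leaves out the catch-all item on investigator judgment.

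1. The etigilimab skin stop and the skin delay share the same grade, relatedness and drug. No duration, recurrence or response condition separates them.
2. The resume bullet lets subjects without a prior Grade 3 skin AE restart at Grade 2 skin toxicity. Taken alone it grants nothing to subjects who did have one. As an exception to the Grade 1 or baseline default, though, its qualifier is needed only if those subjects may also restart, at the default level. It therefore presupposes a restart that the stop list rules out.
3. The closing sentence of 5.1 settles precedence. A subject who meets a stop criterion receives no more therapy, so the stop governs and the delay item can never take effect.
4. In 5.2 the same delay and resume words are coherent, because skin events fall outside the Grade 3 stop. Nothing in 5.1 makes the same carve-out.

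**Electrolyte event (isolated, Grade 4, no sequelae, corrected within 72 hours)**

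| Rule | Result |
|---|---|
| 5.1, position under the stop heading | 1 line, with no words that make it an exemption |
| 5.1, laboratory bullet | No stop: electrolytes are not among the AST, ALT and bilirubin items |
| 5.2, Grade 4 exceptions | 1 named exemption |

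1. The meaning of the 5.1 line depends on nesting. As a top-level bullet it is a stop. As a sub-item of the laboratory exceptions it is also a stop. As a sub-item of the general non-hematologic exceptions it is an exemption.
2. The skin bullet, the laboratory bullet with its two sub-items, and a note on Grade 3 AST or ALT elevation all stand between the line and the general exceptions. The text available does not confirm the indentation.
3. The stop reading gives an odd result: a corrected value is a named stop, while an uncorrected one falls under the laboratory bullet and is not. Unlike the skin and liver bullets, the line also has no verb that requires discontinuation. With the 5.2 wording, this points to an exemption that lost its lead-in. That origin is an inference.

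**The case against.** The strongest reply is that 5.1 resolves its own conflict. The closing sentence makes the stop prevail, and a subject whose etigilimab is delayed may resume only after discussion with the Medical Monitor, so a site cannot re-dose from the delay list alone. Appendix 8 also has a skin algorithm, whose figure is not available here. Most of this stands, and it limits the consequence. It does not remove the contradictory instruction. The Medical Monitor step is written for subjects whose dose is delayed, so it assumes the branch in dispute and gives no rule for choosing between the lists.

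A reader might infer that the same skin case could validly be coded either way. The documents do not support that: once the closing sentence is applied, re-dosing etigilimab is a deviation.

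A reader might also infer that a corrected Grade 4 electrolyte value is definitely a permanent stop, and that re-dosing after it breaches the protocol. The laboratory bullet in the same list says otherwise, and the nesting is unconfirmed.

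The nivolumab comparison has a limit too. The closing sentence speaks of study therapy, not of etigilimab alone, and could be read to reach nivolumab. The comparison here concerns only the stop and delay lists.

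**Conclusion.** The skin contradiction holds on the text and does not depend on layout. One event meets two stop bullets and one delay bullet for etigilimab, the stop governs, and the delay item and the qualifier in the resume bullet should not be there. The electrolyte line conflicts with the laboratory bullet beside it and with 5.2. It is best read as a misplaced exemption, with less certainty because the indentation cannot be confirmed.

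Severity is minor. No number of affected subjects can be given: Section 1.2 reports rash and pruritus among the commonest immune-related events in the earlier study but gives no grades for them, and the documents give no final enrolment. SAP Section 6.3 states that the study was terminated. A reader might infer an effect on ORR through lost or continued exposure. The documents contain nothing from which to estimate one, and none is claimed.

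**What to change.** **Text of Section 5.1**

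- (a) Delete the Grade 3 skin item from the etigilimab dose-delay list, and shorten the resume bullet so that it simply allows restart with Grade 2 skin toxicity. If the sponsor intends a delay, as in 5.2, do the reverse: remove the skin stop bullet and add skin to the exceptions of the general Grade 3 bullet. That choice is a clinical one for the sponsor.
- (b) Reword the electrolyte bullet as an exception that does not require discontinuation, as in 5.2.

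**This study.** Under the governing stop rule, code re-dosing of etigilimab after a Grade 3 drug-related skin AE as a Section 8.8 deviation. Do not code re-dosing after a corrected, isolated Grade 4 electrolyte value as one. Record this at the data review meeting, where SAP Section 10.3 already places the final deviation review.

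**Cost.** The coding rule is one line in the meeting minutes. It needs no new data, because AE Listing 16.2.7 carries grade, relatedness and action taken for each drug. In this study the three edits (delay item, resume bullet, electrolyte bullet) would need an amendment with ethics approval under Appendix 3. With the study terminated, they mainly serve reuse of the text.
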